7. TRIAL TREATMENT / INTERVENTION

7.1. Treatment(s) and Dosing Schedule

The intervention is a therapeutic dose of Cholecalciferol (Oleovit D3 or vitamin D3) versus placebo in an otherwise identical oily solution of MCT, either given by nasogastric or jejunal feeding tube or swallowed. We will use the preparation that is commercially available in Europe (Cholecalciferol, 12.5ml per bottle, 400IU per drop, total dose of 180,000IU per bottle):

- Vitamin D: oral/enteral pharmacological dose of cholecalciferol (vitamin D3)
 - Loading dose of 540,000IU (dissolved in 37.5ml of MCT) followed by 4000IU daily (10 drops) for the entire active trial period (90 days) – total dose 900.000IU
- Placebo: identical regime
 - Loading dose of 37.5ml MCT followed by 10 drops daily

7.1.1. Justification of dosing

In critical illness, there is evidence of rapid falls in circulating vitamin D concentrations potentially due to disrupted metabolism, fluid resuscitation, surgery, and loss of the carrier protein due to hepatic dysfunction (6, 52, 55). There is also evidence that critically ill patients with very low vitamin D concentrations have blunted responses to vitamin D3 replacement. Therefore, a bolus dose is an attractive option to rapidly improve circulating concentrations. The VITdAL-ICU Trial provided an enteral 540,000IU loading dose of vitamin D3 to critically ill adults. This dose increased 25(OH)D from 13 to 35 ng/ml until day 3 and was well tolerated (52). The daily follow-up dose of 4000IU in our trial corresponds to the upper limit recommendation by the IOM (51).

The route chosen is per-oral because currently no high-dose mono-preparation of vitamin D3 is available. Although recently an interventional trial has tested high-dose intramuscular vitamin D3 (56), intramuscular injections may not be feasible in many ICU patients (risk of bleeding and infection).

7.2. Drug Interaction or Contraindications

Inducers of CYP450 metabolic enzymes such as rifampicin, carbamazepine, phenytoin, barbiturates (e.g. phenobarbital, primidone) and glucocorticoids may reduce the efficacy of vitamin D due to increased inactivation. Concomitant use of these medicinal products can increase the vitamin D requirement. Isoniazid may reduce the effectiveness of vitamin D3

due to inhibition of the metabolic activation of vitamin D. Medicinal products leading to fat malabsorption, e.g. orlistat and cholestyramine, may impair the absorption of vitamin D. Increased parathyroid hormone levels can increase the vitamin D metabolism and thus increase the vitamin D requirement.

Concomitant treatment with cardiac glycosides can increase their toxicity due to hypercalcaemia (risk of arrhythmias). Strict medical supervision is needed and, if necessary, monitoring of ECG and serum calcium levels.

Concomitant use of thiazide-type diuretics increases the risk of hypercalcaemia as they reduce the urinary elimination of calcium. In this case, serum calcium levels should be regularly monitored.

Magnesium-containing medicines (e.g. antacids) should not be used during therapy as this may lead to hypermagnesaemia.

Vitamin D3 might increase the intestinal absorption of aluminium.

7.3. Accountability Procedures

At randomisation, the trial treatment number will be provided, and this reference will correspond to a trial treatment pack available in the participating site's pharmacy. The pharmacist will receive notification of the name and trial number of the patient and will prepare the trial treatment for dispensing.

The local pharmacist should keep accurate records of trial drugs dispensed using an Accountability Log provided by the VITDALIZE UK Trial Office. Trial drugs must be kept in the packaging supplied and under no circumstances used for other patients or non-patients.

7.4. Concomitant Vitamin D Supplementation

Routine low-dose vitamin D supplementation (≤800IU/day) is allowed during the trial period and will be documented. This is the current recommended daily allowance (RDA) by the Institute of Medicine. Patients will be advised not to take more than this and the GP will be sent a letter on recruitment advising them of their patient's inclusion in the trial and advice to not prescribe more than the RDA until completion of the trial medication at 90 days. Furthermore, patients will be asked if they took additional supplementation during telephone assessment at day 90.

7.5. Cessation of Treatment / Continuation after the Trial

Patients may discontinue trial treatment at any point if they choose to or if their clinical team feel that continued treatment within the trial is inappropriate. Those who do discontinue trial medication will be asked if they are still willing to be followed-up as part of the trial.

Discontinuation of the trial treatment will be documented on the Electronic Case Report Form (eCRF) and Change of Status Form.

Any patients who decide to discontinue trial treatment, withdraw, or complete follow-up (1 year) will continue their ongoing standard of care pathway.

In instances where the trial treatment has not been administered for 14 days due to misplacement or an adverse reaction, the trial treatment should be withdrawn on the 15th day. A discontinuation of the trial treatment will be documented on the eCRF and Change of Status Form. In addition a file note should be sent to the VITDALIZE Trial Team at BCTU to outline why the trial treatment has been withdrawn.

7.6. Treatment Supply and Storage

Unlabelled Cholecalciferol (Oleovit D3 or vitamin D3) bottles, unfilled identical bottles, and the placebo MCT solution will be provided by Fresenius Kabi Austria GmbH (the marketing authorisation holder for Cholecalciferol).

7.6.1. Treatment Supplies

Distribution of the trial medication to participating centres in the UK will be performed at a certified pharmacy Landesapotheke, [name]. Prior to site activation, the VITDALIZE UK Trial Office will arrange for the supply of high dose vitamin D and placebo to be delivered to the pharmacist of each participating site. Local pharmacists will check the amount and condition of the supply and confirm these details in a Proof of Receipt Form, a copy of which should be provided to the VITDALIZE UK Trial Office.

7.6.2. Packaging and Labelling

A certified pharmacy Landesapotheke, [name] is responsible for labelling and packaging of both the high dose vitamin D preparation and the placebo and for final QP release for clinical trial use (according to Annex 13 guidelines). The labelled and QP released medication will be shipped to trial sites prior to site activation and before the regulatory green light being issued.

7.6.3. Drug Storage

The high dose vitamin D preparation and placebo preparation should not be stored above 25°C and should be kept out of direct sunlight. Temperature monitoring at site will be done according to local standard practice.

At the end of trial or upon expiry of the drug and/or placebo, participating sites can dispose of the trial intervention as per their standard processes following approval from the VITDALIZE UK Trial Office.

In situations where a patient misplaces their trial medication, the patient will be followed up per protocol and be included in the analysis on an intention to treat basis. Patients will not receive any further medication.

8. OUTCOME MEASURES AND TRIAL PROCEDURES

Screening - Day -3 to 0

- Vitamin D analysis
- Eligibility
- Informed consent

Please note, details of the screening assessment have been described earlier in Section 6.2.

Baseline - Day 0

The patient receives the loading dose of the allocated intervention (vitamin D or placebo) and the following is recorded.

- Age
- Sex
- ICU admission diagnosis
- ICU type (medical, surgical, neurological, cardiac)
- Charlson comorbidity index (based on co-morbidities on ICU admission)
- Simplified Acute Physiology Score (SAPS III)
- Therapeutic Intervention Scoring System (TISS 28)
- SOFA score (on admission to ICU)
- Number of organ failures
- Katz Activities of Daily Life (prior to ICU admission)
- Serum calcium
- If applicable¹, patient health-related quality of life questionnaire (EQ-5D-5L and WHODAS 2.0, proxy if patient does not have capacity)
- If applicable², blood sample for future research (pre-intervention)

Please note, if there has been a >24-hour delay since eligibility was confirmed, eligibility must be re-assessed prior to the patient receiving the loading dose.

Please note, the day of the study medication loading dose is the start for the calculation of the time dependent outcome data.

The SOFA and SAPS III scores will also capture data on the presence of sepsis and renal dysfunction (our 2 predefined sub-groups).

Day 1

The patient begins daily dose treatment with allocated intervention for 90 days.

Day 5

- Survival status
- Serum calcium
- Treatment with allocated trial medication
- Trial medication compliance
- SOFA score and type(s) of organ support
- Presence of sepsis/infection
- Targeted adverse events (refer to Section 9.3.2)
- If applicable², blood sample for future research

Day 12

• If applicable², blood sample for future research

Day 28

- Survival status (primary endpoint 28-day mortality)
- Serum calcium (if still in hospital)
- Targeted adverse events (refer to Section 9.3.2)
- Treatment with allocated trial medication
- Trial medication compliance
- If applicable¹, patient health-related quality of life questionnaire (EQ-5D-5L and WHODAS 2.0, proxy if patient does not have capacity)
- If applicable¹, health economics questionnaire

Day 90

- Survival status
- · Katz Activities of Daily Living
- Targeted adverse events (including self-reported infections requiring antibiotics, self-reported falls and fracture, hospital, and ICU admissions)
- Discharge destination
- Trial medication compliance
- If applicable¹, patient health related quality of life (EQ-5D-5L and WHODAS 2.0, proxy if patient does not have capacity)
- If applicable¹, health economics questionnaire

Day 90 marks the end of the trial intervention.

1 year

- Survival status
- If applicable¹, patient health related quality of life (EQ-5D-5L and WHODAS 2.0, proxy if patient does not have capacity)
- If applicable¹, health economics questionnaire

Information obtained at day 28, 90 and 1 year (see above) can be obtained from the hospital's data management systems or via telephone interview with the trial patient or delegated family member. Additional information will be obtained from reviewing hospital clinical records and via NHS Digital and if applicable¹, patient Health economics questionnaire.

The following questionnaires will not be collected for patients recruited post substantial amendment 5 (SA5) implementation:

- EQ-5D-5L
- WHODAS 2.0
- Health economics questionnaire

¹ Only applicable if patient recruited pre-SA5 implementation

² Only applicable if patient recruited pre-SA5 implementation and consents to the sub-study

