8.2. Secondary Outcomes

- 90 day and 1-year mortality
- ICU and hospital mortality
- Hospital and ICU length of stay (starting at day 0, ending at discharge from the trial site or day 90 or mortality, whichever occurs first)
- Change in organ dysfunction on day 5 as measured by Sequential Organ Function Assessment score (SOFA), number of organ failures (0-6; defined as > 2 SOFA points in each of the 6 categories)
- Hospital and ICU readmission until day 90
- Discharge destination (home, rehabilitation, other hospital)
- Katz Activities of Daily Life at day 90
- Self-reported infections requiring antibiotics until day 90
- Health-related quality of life (EQ-5D-5L) at 90 days and 1 year¹
- Disability assessment (WHODAS 2.0) at 90 days and 1 year¹
- Secondary health care utilisation in the first year (ICU and hospital length of stay, readmissions and utilisation of hospital and community care resources after hospital discharge 1 year after randomisation), from Hospital Episode Statistics, civil registry data held by NHS Digital and patient questionnaires¹
- Health economics analysis¹
 - Cost effectiveness of screening for and treating VDD in critical illness
 - Cost per quality-adjusted life year gained 1 year after randomisation and at end of life

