14.3.5. Subgroup Analyses

The effect of high dose vitamin D versus placebo will be evaluated in the following *a priori* subgroups: i) patients with sepsis (admission diagnosis) vs non-sepsis (based on the evidence that vitamin D has antimicrobial properties that may benefit this population in particular (16); ii) kidney function, CKD 4 (eGFR<30mL/min/1.73m2) or lower vs higher (based on the possible effect of pre-existing CKD and VDD on increased mortality and alternate metabolism of vitamin D3 (cholecalciferol); iv) COVID-19 or Non-COVID-19 patients.

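### The renal subgroup is defined by pre-existing CKD 4, but the protocol names acute scores as its data source, so acute kidney injury could be classed as CKD

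*Protocol*

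**What the plan says.** Section 14.3.5 of the protocol lists the renal subgroup as "kidney function, CKD 4 (eGFR<30mL/min/1.73m2) or lower vs higher". Its reason is "based on the possible effect of pre-existing CKD and VDD on increased mortality", together with a possible change in how vitamin D3 is metabolised.

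Section 8, in the note under the day 0 list, says where the data come from: "The SOFA and SAPS III scores will also capture data on the presence of sepsis and renal dysfunction". It adds in brackets that these are the trial's two predefined subgroups.

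The same day 0 list records "SOFA score (on admission to ICU") and "Simplified Acute Physiology Score (SAPS III"). Section 8.2 uses SOFA again as an outcome: "Change in organ dysfunction on day 5 as measured by Sequential Organ Function Assessment score (SOFA").

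The day 0 list also has an item on earlier disease, "Charlson comorbidity index (based on co-morbidities on ICU admission"), but nothing in the protocol links it to the renal subgroup. Neither the day 0 list nor the schedule in Section 8.5 contains a pre-admission creatinine or eGFR, or a CKD stage.

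**The concern.** The subgroup exists to ask whether the effect of vitamin D differs in patients who already had advanced chronic kidney disease. The source named for it describes the kidney during the acute illness. One reading of renal function at ICU admission cannot by itself separate a patient with long-standing CKD 4 from one whose kidneys were normal the week before. Acute injury is foreseeable here: Section 1.1 cites it among the conditions associated with vitamin D deficiency.

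Two errors of interpretation could follow. A difference driven by acute severity could be published as a CKD effect, and a real difference by CKD could be hidden because the CKD group is mixed with patients who do not have the disease.

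**Working it through.** **Comparing the sections.** The protocol states no figure for the size or make-up of this subgroup, so there is nothing to reproduce. The check is first one of wording.

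| Feature | Section 14.3.5 | Section 8 |
|---|---|---|
| Construct | CKD 4, eGFR below 30 | renal dysfunction |
| Time it refers to | before the acute illness | ICU admission for SOFA; no separate time stated for SAPS III |
| Source | none named | SOFA and SAPS III |
| Number of predefined subgroups | three (numbered i, ii, iv) | two |

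That SOFA and SAPS III are acute measures follows from the protocol's own use of them: SOFA is expected to change by day 5, and SAPS III is an acute physiology score by name. The definition and the named source therefore describe different things. The different subgroup counts suggest that the two sections were not updated together. A footnote to the table of non-expedited events (Section 9.3.2) adds to the ambiguity, because it uses the CKD 4 threshold for a change in kidney function during the trial.

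**How far this could matter.** Let c be the share of patients with pre-existing CKD 4 or worse, and a the share of the remaining patients flagged because of acute renal dysfunction. Assume that every true CKD patient is flagged. The share P of the flagged group with true CKD is

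P = c / (c + (1 − c) × a).

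The documents give neither c nor a. The values below are assumptions chosen to span a wide range.

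| c | a = 5% | a = 10% | a = 20% | a = 30% | a = 40% |
|---|---|---|---|---|---|
| 2% | 29% | 17% | 9% | 6% | 5% |
| 5% | 51% | 34% | 21% | 15% | 12% |
| 10% | 69% | 53% | 36% | 27% | 22% |
| 15% | 78% | 64% | 47% | 37% | 31% |

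Example: c = 5% and a = 20% gives 0.05 / (0.05 + 0.95 × 0.20) = 0.05 / 0.24 = 21%. With the planned 2400 patients, that is 120 with CKD among 576 flagged.

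P falls below one half when a exceeds c / (1 − c), which is 2.0%, 5.3%, 11.1% and 17.6% for the four rows. This happens in 15 of the 20 cells.

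**Effect on the subgroup contrast.** Write the treatment effect as θ1 in CKD, θ2 in acute renal dysfunction without CKD, and θ0 in everyone else. Treating effects as averaging across patients, the flagged-minus-unflagged contrast is approximately

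P(θ1 − θ0) + (1 − P)(θ2 − θ0).

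- If θ2 = θ0, a true CKD difference shrinks by the factor P.
- If θ1 = θ0 but θ2 ≠ θ0, a difference appears although CKD plays no part.

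Both occur to some degree whenever a is above zero. Only their size depends on the assumed values.

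**The case against.** The strongest reply is that Section 8 says only that the scores capture data on renal dysfunction. It does not say that they alone decide who is in the subgroup. The definition in Section 14.3.5 is an eGFR threshold, Section 14.2 calls its text a brief outline, and the choice of variable is commonly left to the statistical analysis plan. This stands in part. A reader might infer that the protocol makes SOFA and SAPS III the sole classifier, and it does not say that. But the point is not missing detail: the protocol names a source that does not fit its own definition. An analysis plan that follows one section departs from the other.

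A second reply is that acute renal function is not foreign to the rationale. Section 14.3.5 introduces the subgroup as kidney function and mentions altered vitamin D metabolism, and Section 1.1 lists reduced renal conversion among the possible reasons for falling vitamin D levels in critical illness. That is fair, and it supports studying acute dysfunction as a separate question. It does not make acute dysfunction a measure of pre-existing CKD, which is the reason given for this subgroup.

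A reader might also infer that most patients in the subgroup would not have CKD. The documents do not support that as a finding. It needs prevalences that they do not give, and it fails in 5 of the 20 combinations above, for example at c = 10% and a = 10% (53% with CKD).

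**Conclusion.** The inconsistency between Sections 8 and 14.3.5 is real. If the source named in Section 8 is followed, patients with acute kidney injury and no prior CKD enter the CKD 4 group, a true CKD difference is diluted, and a difference by acute severity may be read as a CKD effect.

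The extent is not known. Under the assumed ranges, true CKD is between 5% and 78% of the flagged group, given that all true CKD patients are flagged. Shrinkage of the contrast by that same factor needs the further assumption that acute dysfunction without CKD does not itself change the treatment effect.

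The consequence is limited to the interpretation of one a priori subgroup. The primary analysis and the sample size are unaffected. It is worth correcting because it is cheap to settle now and hard to defend once results by arm are known.

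**What to change.** Reconcile Sections 8 and 14.3.5 before unblinding:

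- Remove SOFA and SAPS III as the source for the CKD subgroup, and correct the count of predefined subgroups in the same note.
- Classify the subgroup from pre-existing renal disease recorded in the comorbidity data already collected at baseline for the Charlson index. Use a pre-illness eGFR only where one is already available.
- If acute renal dysfunction at admission is also of interest, analyse it as a separate subgroup and label it as such.

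The cost is mainly wording, because the comorbidity data are already recorded. Three limits remain. The protocol does not list the comorbidity fields, so their renal content must be checked on the case report form. The record may not match eGFR below 30 exactly, so the subgroup label should state what was used. Pre-illness eGFR is not a scheduled item and cannot be assumed for all patients. Since the sponsor writes the main analysis plan (Section 14.2), the definition has to be agreed for the international trial and not only in the UK text.

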8.1. Primary Outcome

• All-cause mortality at 28 days after randomisation

8.2. Secondary Outcomes

- 90 day and 1-year mortality
- ICU and hospital mortality
- Hospital and ICU length of stay (starting at day 0, ending at discharge from the trial site or day 90 or mortality, whichever occurs first)
- Change in organ dysfunction on day 5 as measured by Sequential Organ Function Assessment score (SOFA), number of organ failures (0-6; defined as > 2 SOFA points in each of the 6 categories)
- Hospital and ICU readmission until day 90
- Discharge destination (home, rehabilitation, other hospital)
- Katz Activities of Daily Life at day 90
- Self-reported infections requiring antibiotics until day 90
- Health-related quality of life (EQ-5D-5L) at 90 days and 1 year¹
- Disability assessment (WHODAS 2.0) at 90 days and 1 year¹
- Secondary health care utilisation in the first year (ICU and hospital length of stay, readmissions and utilisation of hospital and community care resources after hospital discharge 1 year after randomisation), from Hospital Episode Statistics, civil registry data held by NHS Digital and patient questionnaires¹
- Health economics analysis¹
 - Cost effectiveness of screening for and treating VDD in critical illness
 - Cost per quality-adjusted life year gained 1 year after randomisation and at end of life

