2. AIMS AND OBJECTIVES

2.1. Aims and Objectives

Overall aim

Our aim is to conduct the UK arm of a large international randomised controlled trial to determine if treatment with high dose vitamin D improves patient outcomes and is cost-effective, in comparison to placebo in severely VDD critically ill adult patients admitted to ICU.

Primary objective

The primary objective of this trial is to determine whether treating severe VDD with high dose oral vitamin D3 replacement in adult critically ill patients decreases 28-day mortality.

Secondary objectives

The secondary objectives of the overarching trial are to determine whether treating severe VDD with high dose oral vitamin D3 replacement in adult critically ill patients:

- Reduces organ dysfunction
- Reduces hospital and ICU length of stay and mortality
- Improves long-term survival
- Reduces readmission to hospital
- Improves activities of daily living
- Improves health-related quality of life at 90 days and 1 year
- Reduces disability at 90 days and 1 year
- Reduces health care utilisation to 1 year
- Is cost-effective in the NHS setting

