14. STATISTICAL CONSIDERATIONS

14.1. Sample Size

The sample size for the multinational trial is based on the primary endpoint 28-day mortality. In the VITdAL-ICU trial, in the pre-defined subgroup with severe VDD, 28-day mortality rates of 36% (37/102) in the placebo group and 20% (20/98) in the vitamin D group were observed (51). The VITDALIZE trial has been designed to be powered to detect a smaller, but clinically relevant absolute mortality difference of 5% with a power of 80% or a 6% difference with 90% power with an assumed baseline mortality rate of 25% (close to the lower limit of the 95% CI of the 36% mortality observed in VITdAL-ICU). This corresponds to a clinically important relative risk reduction of between 20% and 24%. Using a fixed sample size design and a 2-sided log-rank test for equality of survival curves with a 2-sided alpha level of 5%, a sample size of over 1000 patients per group will be needed (total sample size of approximately 2200). The table below shows this, and varies the baseline event rate from 25% to 30% to illustrate that our assumptions are robust to modest variations in our assumptions.

Placebo 28-day all-cause mortality	25%		30%	
	80% power	90% power	80% power	90% power
VitD 28-day all-cause mortality	20%	19%	25%	24%
Hazard ratio	0.78	0.73	0.81	0.77
N = (per group)	1093	1002	1248	1149
Total number of events required	486	434	686	620
N = (total)	2186	2004	2496	2298

Accounting for a drop-out rate of approximately 10% yields a total sample size of N=2400 patients with the UK contributing 25% of the sample size with 600 patients. Loss to follow up in critical care trials for 28-day mortality is low and is approximately 3% in previously published critical care trials (51, 56, 57) so this 10% estimate of loss to follow up is also conservative.

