14.2. Analysis of Outcome Measures

A separate Statistical Analysis Plan (SAP) will be produced by the Sponsor outlining the analysis of VITDALIZE, the UK specific outcomes will be appended to the SAP completed by the UK Statistician in collaboration with the UK CI. The SAP will provide a more comprehensive description of the planned statistical analyses. A brief outline of these analyses is given below. The primary comparison groups will be composed of those treated with vitamin D3 versus those treated with placebo.

Intention-to-treat (ITT) population: The primary analysis will be performed on the ITT population. The ITT population will include all patients who receive at least the loading dose of the trial medication. All patients included here will be analysed according to the treatment assignment during randomisation.

Per protocol population: The per protocol population will include all patients who received the loading dose and have a compliance >80%. Compliance is defined as self-reported percentage of doses ingested until day 90. Other protocol violations may also lead to exclusion of patients from the per protocol population. This will be discussed on an individual basis within the international trial's teams working on VITDALIZE.

Safety population: The safety analyses will be based on the treated set, which is defined as all randomised patients who receive at least 1 dose of trial medication. All patients will be analysed according to the treatment they received.

All available data will be used in the analyses and data summaries. There will be no imputation of any missing data. All outcomes will be adjusted for the baseline values (where available) and the stratification parameters (gender and centre). If covariate adjustment is not practical, then unadjusted estimates will be produced and it will be made clear in the output why this occurred, e.g. due to lack of model convergence.

14.3. **Data analysis**

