14.3.4. Secondary Outcome Measures

ICU, hospital mortality, 90-day mortality and 1-year mortality will be analysed using the same methods as described for the primary outcome. For any other secondary outcomes that are continuous, these will be analysed using mixed effects linear regression model. The safety outcomes, (hypercalcemia on day 5, new kidney stones, self-reported falls, and fractures until day 90) will be analysed as binary variables and compared using a mixed effects binomial model.

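### Length of stay ends at death and falls under the linear-model rule, so a mortality benefit biases the comparison towards longer stay on vitamin D

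*Protocol*

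**What the plan says.** The protocol's section 8.2 counts hospital and ICU length of stay from day 0, "ending at discharge from the trial site or day 90 or mortality, whichever occurs first". The outcome list in the trial summary gives the same end rule and identifies day 0 as the day of randomisation.

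Section 14.3.4 assigns methods in two steps. First, "ICU, hospital mortality, 90-day mortality and 1-year mortality will be analysed using the same methods as described for the primary outcome", that is, Kaplan-Meier curves and a Cox model with centre as a random effect. Then comes a general rule: "For any other secondary outcomes that are continuous, these will be analysed using mixed effects linear regression model". Length of stay is not mentioned by name. As a count of days it is a continuous outcome other than mortality, so the general rule covers it.

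Section 2.1 lists as one objective that treatment "Reduces hospital and ICU length of stay and mortality". The protocol nowhere treats death as a competing event for discharge, and it does not define a stay outcome that separates live discharge from death.

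**The concern.** Under this definition, death closes a stay in the same way as going home. A patient who dies on day 3 contributes 3 days; one who recovers and leaves on day 10 contributes 10. In a linear model of the mean, the death is the more favourable value.

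A patient whose in-hospital death is prevented was still in hospital when that death would have occurred, so survival normally adds days to the recorded stay. The two halves of the section 2.1 objective then pull against each other in the stay analysis: the mortality effect the trial is powered to find pushes mean stay upwards on vitamin D. A real but small shortening of stay among survivors could be hidden, and a treatment with no effect on survivors' stay would tend to look as if it prolonged it.

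**Working it through.** **The plan's own figure.** The protocol states no figure for length of stay, but the mortality inputs come from its sample size calculation, so that was checked first. Section 14.1 uses an "assumed baseline mortality rate of 25" per cent, an "absolute mortality difference of 5% with a power of 80% or a 6% difference with 90% power", and a "2-sided log-rank test for equality of survival curves with a 2-sided alpha level of 5" per cent. For 25% versus 20%:

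- Hazard ratio = ln(0.80)/ln(0.75) = 0.776 (stated 0.78).
- Schoenfeld: 487 events; 487/(2 × 0.225) gives 1083 per group.
- Freedman: 492 events, 1094 per group.
- Stated: 486 events, 1093 per group. Both methods agree to within 3%, and the other three columns of the table also reproduce.

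**Bias in mean stay.** Let S be the mean stay of survivors, D the mean recorded stay of those who die, and pC and pT the mortality on placebo and vitamin D. If treatment does not change S or D:

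- placebo mean = (1 − pC)·S + pC·D
- vitamin D mean = (1 − pT)·S + pT·D
- difference = (pC − pT)·(S − D)

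A true cut of c days in survivors' stay subtracts (1 − pT)·c. It is fully masked when c = (pC − pT)·(S − D)/(1 − pT).

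S and D are assumptions, because the protocol gives neither.

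| S / D (days) | Shift, 25% v 20% | Shift, 25% v 19% | Cut masked at 25% v 20% |
|---|---|---|---|
| 20 / 15 | 0.05 × 5 = +0.25 | +0.30 | 0.31 days (1.6%) |
| 20 / 8 | 0.05 × 12 = +0.60 | +0.72 | 0.75 days (3.75%) |
| 25 / 10 | 0.05 × 15 = +0.75 | +0.90 | 0.75/0.80 = 0.94 days (3.75%) |
| 30 / 10 | 0.05 × 20 = +1.00 | +1.20 | 1.25 days (4.2%) |

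The direction depends on D being shorter than S. If both were 20 days the shift would be zero; with S = 15 and D = 20 it would be −0.25 day.

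**Simulation.** There were 2000 runs with 1080 per arm (2400 × 0.90 / 2) and mortality 25% versus 20%. Survivors' stays were gamma (shape 1.5, mean 25, capped at day 90); times to death were exponential (mean 10, capped at day 28).

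- No effect on survivors' stay: mean difference +0.77 days (the caps move it slightly from +0.75). The estimate favours placebo in 83% of runs and is significantly longer on vitamin D in 17%.
- True 4% cut in survivors' stay: mean difference −0.02 days, so the benefit disappears.
- True 10% cut: mean difference −1.14 days. The sign is right but the effect is diluted: before capping, the cut alone is worth 0.80 × 2.5 = 2.0 days.

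**The case against.** The best reply is that the linear model reaches length of stay only by inference. Section 14.3.4 does not name it, the end rule in section 8.2 reads like a time-to-event definition, and section 14.2 describes its account as an outline that the SAP will expand. That lowers confidence a little. It does not remove the point, because the protocol does state an end rule and a method, and the natural reading joins them. If the SAP differs, the two need reconciling.

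Second, mean bed-days ending at death is a legitimate quantity. Section 14.5 costs ICU and hospital stay, and for costing, a stay that ends at death should be counted as such. Mortality is also reported separately, so a reader can see both effects. This stands, and is a reason to keep the measure for resource use. It does not make the mean a fair test of whether treatment shortens stay.

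A reader might also infer stronger conclusions that the documents do not support:

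- That an effective drug must appear to lengthen stay. This holds only if survivors' stay is nearly unchanged; a 10% cut still shows the right sign.
- That the bias could be several days, using the 17.5-point hospital mortality difference quoted in section 1.2. The protocol calls that subgroup result hypothesis generating, and section 14.1 plans for 5 to 6 points.
- That skew and the day-90 cap invalidate the model. With over 1000 per group a difference in means is estimable; the difficulty is what that mean measures.
- That day-5 SOFA and day-90 Katz are distorted too, because "There will be no imputation of any missing data". The protocol does not say whether death counts as missing for these scores or how the dead would be scored, and it does not class Katz or the organ-failure count as continuous.

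**Conclusion.** The point holds for length of stay alone, as a bias towards longer stay on vitamin D when vitamin D reduces mortality. At the 5-point design effect it is about +0.25 to +1.0 day, and at 6 points +0.3 to +1.2 days. With mean stays of 25 and 10 days it would mask a true cut of roughly 4% in survivors' stay.

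These sizes rest on assumed mean stays, on patients saved having the same mean stay as other survivors, and on applying a 28-day mortality difference to an outcome that runs to day 90. The bias is modest and need not reverse the sign. The primary analysis and the sample size are not affected. It should be fixed, because it concerns a named secondary objective, but it does not threaten the trial's main conclusion.

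**What to change.** In section 14.3.4, exempt hospital and ICU length of stay from the linear-model rule. Analyse time to discharge alive, for ICU and hospital separately, up to day 90 with death as a competing event. Report cumulative incidence of live discharge by arm and a hazard ratio adjusted for sex and centre, stating which hazard is meant, and read the result beside mortality. On the cumulative incidence scale a death is never counted as a discharge, so fewer deaths no longer count against the treatment. Mean bed-days may stay as a descriptive or resource-use measure, with its purpose stated.

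The cost is a wording change in the protocol, matched in the SAP. No new data are needed, since the current definition already requires the discharge and death dates. The change should be made before unblinding, so that it cannot look like a response to the result. The drawback is that a hazard ratio is less intuitive than a difference in days.
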